4.1 Method of Assigning Subjects to Treatment Groups

Subjects who meet the entry criteria for itching and redness response to the CAC at Visits 2, 3a, 3b, and 4a will be randomized at a 1:1 ratio (active:vehicle) at Visit 4b (Day 1) to receive one of the following treatment arms bilaterally:

- OTX-DP (N=40 subjects) or
- PV (N=40 subjects)

4.2 Masking and Unmasking

In the case of a medical emergency or occurrence of a serious adverse event (SAE), the randomization code may be unmasked and made available to the Investigator, Sponsor, and/or other study personnel involved in the conduct of the study. In the absence of medical need, the randomization code will not be available to the above individuals until after the study is completed and the database is locked.

In the event of a medical need, the Investigator will treat each subject, as medically required. If the Investigator feels it is necessary to unmask a subject's treatment assignment after an emergency situation, the Investigator may call the Medical Monitor and notify the Sponsor. The treatment assignment will be revealed on a subject-by-subject basis with the approval of the Medical Monitor and Sponsor, leaving the masking of the remaining subjects intact.

The site will receive one emergency unmasking envelope for every product received and the envelopes should be stored in a secured location. The envelopes and product will both be labeled with the same randomization number. The envelopes are sealed and contain the unmasked treatment information for the corresponding study product.

Ocular Therapeutix will make the final determination if the unmasking request will be granted. Once the unmasking request is granted the Investigator or designee should identify and retrieve the emergency unmasking envelope for the given subject. The emergency unmasking envelope should be opened by the designated site personnel. The Investigator must also indicate in source documents and in the electronic case report form (eCRF) that the mask was broken and provide the date, time, and reason for breaking the mask. Any AE or SAE associated with breaking the mask must be recorded and reported as specified in this protocol.

Subjects will have the investigational product (IP) removed immediately if treatment assignment is unmasked.

5. Sample Size and Power Considerations

Approximately 80 subjects will be randomized at Visit 4b in a 1:1 ratio across the two treatment arms (40 OTX-DP; 40 PV). Up to approximately 10 additional subjects may be enrolled to make up for any subjects who did not complete Visit 6b CAC procedures.

A total of 40 subjects in each treatment arm will provide 97.0%, 99.8%, and 99.9% power to demonstrate a statistically significant difference in ocular itching between OTX-DP and PV treated subjects at each of the 3-, 5-, and 7-minute post-CAC time points of Visit 6b, respectively, assuming a treatment difference of 0.87 units at 3 minutes post-CAC, 1.08 units at 5 minutes post-CAC, and 1.13 units at 7 minutes post-CAC; a standard deviation of 1.0 unit at all time points; and a two-sided Type I error of 0.05.

Assuming independence between time points, 40 subjects per group will have at least 96.7% power to demonstrate a statistically significant difference over all three primary post-CAC time points at Visit 6b for ocular itching between OTX-DP and PV treated subjects.

6. Data Preparation

6.1 Input Data

Study data will be recorded on the eCRFs supplied by Statistics & Data Corporation (SDC) using IBM clinical, version 2019.4.0.1. When all prerequisites for database lock have been met, the database will be locked. Following database lock, approval will be obtained from the Sponsor to unmask the study. Any changes to the database after data have been locked can only be made with the approval of the Sponsor in consultation with SDC.

Final analysis will be carried out after the following have occurred:

- Protocol deviations have been identified and status defined (major/minor deviations).
- Analysis populations have been determined.
- Database lock has occurred.
- Randomized treatment codes have been unmasked.

6.2 Output Data

Data from IBM clinical will be transferred to SDC Biostatistics and incorporated into standard formats following the Study Data Tabulation Model (SDTM). Data will then be mapped to analysis datasets using the Analysis Data Model (ADaM). Both SDTM- and ADaM-formatted data will be used to create the subject listings, while all tables and figures will be based on the ADaM-formatted data.

SDTM will follow the SDTM version 1.4 model and will be implemented using the SDTM Implementation Guide version 3.2 and the SDTM Controlled Terminology version 2016-06-24. ADaM data will follow the ADaM version 2.1 model and will be implemented using the ADaM Implementation Guide version 1.3. Both SDTM and ADaM will be validated using Pinnacle 21 version 2.2. Any discrepancies in the validation will be noted in reviewer's guides accompanying the final data transfers.

Define.xml will be created for SDTM and ADaM using the Define-XML version 2.0 model.

7. Analysis Populations

7.1 Intent-to-Treat

The Intent-to-Treat (ITT) population consists of all subjects who are randomized. All data will be included and no subjects will be excluded because of protocol violations. The ITT population will be analyzed as randomized and will be used for the efficacy analyses.

7.2 Per Protocol

The Per-Protocol (PP) population is a subset of the ITT population and includes the subjects who completed the study through Visit 6b (Day 8; 7 days post-insertion; 8 hours from Visit 6a) with no major protocol violations that would impact the efficacy of the drug. Protocol deviations will be assessed and decisions regarding subject evaluability will be made prior to database lock and unmasking. This population will be analyzed as treated using observed data only for confirmatory analyses.

7.3 Safety

The Safety population includes all randomized subjects who received the IP. The Safety population will be analyzed as treated and will be used for the safety analyses. No data will be excluded for any reason.

8. General Statistical Considerations

8.1 Unit of Analysis

The subject will be considered the unit of analysis for all efficacy variables (e.g., itching, redness). In cases where data are collected for each eye, the average of both eyes of each subject will be used for statistical summaries and analyses. Medical history, concomitant medications, and AEs will also be collected and presented at the subject level.

The eye will be considered the unit analysis for all safety variables (e.g., BCVA, IOP).

8.2 Missing or Inconclusive Data Handling

8.2.1 Imputation of Primary and Key Secondary Efficacy Variables

The impact of missing data on the primary and key secondary efficacy endpoints will be explored using the following variety of missing data handling techniques:

- Markov chain Monte Carlo (MCMC) multiple imputations
- Last observation carried forward (LOCF)
- Baseline observation carried forward (BOCF)
- Worst case observation (WCO)

Details related to the MCMC multiple imputation procedures are included in Section 12.1 as this imputation method will be used for the primary efficacy analysis. The screening visits (Visit 1, Visit 2, Visit 3a, Visit 3b and Visit 4a) will not be imputed nor summarized in the MCMC tables.

For the LOCF imputation, only post-challenge observations within the same visit will be carried forward. For example, there must be a 3-minute, post-CAC value at each visit available to implement LOCF at that visit. However, in the case that the 3-minute, post-CAC value is missing, only the subsequent non-missing assessments will be used in the analysis. The screening visits (Visit 1, Visit 2, Visit 3a, Visit 3b and Visit 4a) will not be imputed nor summarized in the LOCF table.

For the BOCF imputation, missing data post-baseline will be imputed with the time appropriate baseline data from Visit 4a. For example, if a subject's 3-minute, post-CAC value is missing at Visit 6b, then that subject's 3-minute, post-CAC value from Visit 4a will be used in its place. The screening visits (Visit 1, Visit 2, Visit 3a, Visit 3b and Visit 4a) will not be imputed nor summarized in the BOCF table.

For the WCO imputation, missing data due to a subject being prescribed anti-inflammatory or anti-allergy (rescue) medication will be imputed using the worst possible outcome (maximum observed value) from the subject's treatment group at the given visit and time point, starting at the first time point at which a subject takes an anti-inflammatory or anti-allergy medication. No other missing data will be imputed. Specific anti-inflammatory and anti-allergy medications triggering the WCO imputation will be identified prior to database lock by the study team. The screening visits (Visit 1, Visit 2, Visit 3a, Visit 3b and Visit 4a) will not be imputed nor summarized in the WCO table.

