#### 7.7. **Rescue Therapy**

Cold compress should first be used in the management of allergic symptoms. Subjects may be prescribed anti-inflammatory or anti-allergy medication at the Investigator's discretion. If prescribed such anti-inflammatory or anti-allergy medication, the insert will not be removed and subjects will be followed for safety only.

Currently marketed over-the-counter anti-allergy eye drops (i.e., anti-histamine/ vasoconstrictor combination products such as Visine®-A®) may be administered to subjects at the end of the subject's last visit, after all evaluations are completed.

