## **10.7.** General Imputation Methods

Missing data for the primary efficacy variable will be imputed using Markov Chain Monte Carlo (MCMC) multiple imputation techniques on the ITT population, producing twenty "complete" (imputed) datasets which will then be analyzed separately. Results from the separate analyses on the twenty "complete" datasets will be combined for presentation through the use of SAS PROC

CLN-Protocol-0052 Page **41** of **61** 

MIANALYZE. A separate imputation model will be fit for each time point. The model will include variables for treatment, baseline measure, and response measure.

For sensitivity analysis, the ITT population will also be analyzed using the following:

- Observed data only
- Last observation carried forward (LOCF)
- Worst case observation (WCO)
- Baseline observation carried forward (BOCF)

For the LOCF imputation, only post-challenge observations within the same visit will be carried forward. Therefore, there must be post-challenge values available at post-baseline visits to implement LOCF, as pre-challenge values will not be carried forward to post-challenge values and the prior visit values will not be carried forward to the following visit values. Missing values post-challenge will be carried forward from the last observed time point within the same visit, i.e., a missing 5-minute observation at Visit 5b will be imputed from the 3-minute observation from Visit 5b, etc.

For the WCO imputation, missing data due to a subject being prescribed anti-inflammatory or antiallergy medication will be imputed using the worst possible outcome (maximum observed value) from the subject's treatment group, starting at the first time point at which a subject takes an antiinflammatory or anti-allergy medication.

For the BOCF imputation, missing data post-baseline will be imputed with the corresponding time point baseline data from Visit 4a.

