2.1 Study Variables

2.2 Primary Variables

The primary efficacy variable is:

Ocular itching evaluated by the subject on Visit 6b (Day 8; 7 days post-insertion; 8 hours from Visit 6a) at 3(±1), 5(±1), and 7(±1) minutes post conjunctival allergen challenge (CAC) (0-4 scale, allowing half unit increments).

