ODS OUTPUT STATISTICS = OUTPUTDF;
RUN;
PROC MIANALYZE DATA = OUTPUTDF;
BY VISIT TIME CLASS;
MODELEFFECTS MEAN;
STDERR STDERR;
RUN;
```

The following SAS code will be used for the Wilcoxon rank sum test:

```
ODS OUTPUT WILCOXONSCORES = WILCOXON (WHERE=(CLASS=:"1"));
PROC NPAR1WAY DATA = INDATA WILCOXON;
    BY VISIT TIME IMPUTATION ;
    CLASS TREATMENT;
    VAR SCORE;
RUN;
DATA WILCOXON;
  SET WILCOXON;
  BY VISIT TIME;
  MEAN = (SUMOFSCORES - EXPECTEDSUM) /N;
  STDERR = STDDEVOFSUM/N;
RUN;
PROC MIANALYZE DATA = WILCOXON ALPHA = 0.05;
BY VISIT TIME;
MODELEFFECTS MEAN;
STDERR STDERR;
RUN;
```

The ordering of the above code should be adjusted accordingly for the real data, to make sure the tests are performed to compare the treatment group vs. the placebo group.

Sensitivity or supportive analyses will be performed on the ITT population using LOCF, BOCF, and WCO imputations as well as observed data only (see Section 8.2.1 for additional data imputation details). The primary analysis will also be repeated on the PP population with observed data only.

A line graph will be produced to show mean (+/- standard error [SE]) ocular itching score by treatment group (OTX-DP, PV), visit (Visit 6b, Visit 8b), and time point (3, 5, and 7 minutes post-CAC). Mean change from baseline (+/- SE) for each treatment arm will be presented in a similar figure. Both figures will be presented separately for the ITT population using observed data only.

A listing of ocular itching scores for all subjects will also be provided.

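### The worst-case imputation takes its value from the subject's own arm, so if OTX-DP works, rescued OTX-DP subjects tend to get a milder penalty than rescued PV subjects

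*SAP*

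**What the plan says.** Rescued subjects drop out of the efficacy assessments: under Protocol 7.7, "the insert will not be removed and subjects will be followed for safety only". Their later challenge scores are therefore missing.

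The worst case observation (WCO) rule in SAP 8.2.1 fills these scores with the "worst possible outcome (maximum observed value) from the subject's treatment group at the given visit and time point". Protocol 10.7 has the same own-arm rule, "worst possible outcome (maximum observed value) from the subject's treatment group, starting at the first time point", but does not tie the maximum to a visit and time point. Neither document offers a value common to both arms. The outcome is scored on a "0-4 scale, allowing half unit increments" (SAP 2.2).

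Two statements limit the role of WCO. It covers rescue only: "No other missing data will be imputed". It is also supportive, since SAP 12.1 states: "Sensitivity or supportive analyses will be performed on the ITT population using LOCF, BOCF, and WCO imputations as well as observed data only". Of MCMC multiple imputation, SAP 8.2.1 says that "this imputation method will be used for the primary efficacy analysis". SAP 12.2.1 carries the same set of imputations over to the key secondary visits.

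**The concern.** The wording equates two different things. The worst possible score is 4, whereas the highest score seen in one arm depends on how well that arm did. If OTX-DP reduces itching, the whole distribution in that arm shifts down, and its maximum tends to shift with it. The same event, needing rescue, is then scored more kindly in the active arm.

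This matters because WCO is the only planned analysis written specifically for rescue. The MCMC model includes treatment, so it imputes a rescued OTX-DP subject from the relation seen in that arm. The observed-data analysis drops the subject. LOCF carries values only within a visit, so it does nothing for a subject with no scores at that visit. A reader of the study report would look to WCO for the strictest handling of rescue, and the own-arm rule softens it on the side being tested.

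**Working it through.** **Inputs from the documents.** 40 per arm; differences of 0.87, 1.08 and 1.13 at 3, 5 and 7 minutes; SD 1.0; two-sided 0.05 (SAP 5). Scale 0 to 4 (SAP 2.2). Two-eye averages move in steps of 0.25 (SAP 12.1).

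**Assumptions not in the documents.** PV mean at Visit 6b of 2.0, 2.5 or 3.0; 4 of 40 rescued per arm, with 2 as an alternative; normal scores rounded to 0.25 and clipped to 0–4; rescue unrelated to the score.

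**Step 1: the plan's own figure.** For a two-sample t-test with 78 degrees of freedom, the noncentrality is d/√(2/40):
- 0.87/0.2236 = 3.89, power 97.0%
- 1.08/0.2236 = 4.83, power 99.75%
- 1.13/0.2236 = 5.05, power 99.88%

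The product is 96.65%. This reproduces the stated 97.0%, 99.8%, 99.9% and 96.7%.

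**Step 2: size of the lean.** With k subjects rescued in the OTX-DP arm, replacing that arm's maximum by a common maximum raises the OTX-DP mean by k × (common maximum − OTX-DP maximum)/40. The PV mean hardly moves, because PV usually supplies the common maximum. Expected maxima come from 20,000 simulated trials with 36 observed per arm.

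| PV mean (assumed) | Difference | OTX-DP max | PV max | P(OTX-DP max lower) | Lean with k = 4 |
|---|---|---|---|---|---|
| 2.0 | 0.87 | 3.23 | 3.87 | 83% | 4 × 0.64/40 = 0.064 |
| 2.5 | 0.87 | 3.65 | 3.99 | 63% | 4 × 0.34/40 = 0.034 |
| 3.0 | 0.87 | 3.92 | 4.00 | 22% | 4 × 0.08/40 = 0.008 |
| 2.5 | 1.13 | 3.44 | 3.99 | 79% | 4 × 0.55/40 = 0.055 |
| 3.0 | 1.13 | 3.80 | 4.00 | 44% | 4 × 0.20/40 = 0.020 |

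The largest value on this grid, about 0.09, is at PV mean 2.0 and difference 1.13, where the OTX-DP maximum is lower in 92% of trials.

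The simulated differences (OTX-DP minus PV) at a planned 0.87 agree. Moving from the own-arm to the pooled maximum changes them as follows:
- PV mean 2.0: −0.790 to −0.726; single-time-point power 91.4% to 86.7%
- PV mean 2.5: −0.776 to −0.742; power 91.6% to 89.8%
- PV mean 3.0: −0.722 to −0.714; power 92.0% to 91.8%

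With 2 rescued per arm the shifts are 0.031, 0.016 and 0.004. Widening the grid to PV means of 1.5 to 3.0, SD 0.8 to 1.0 and 2 to 4 rescued per arm gives about 0.003 to 0.113.

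**Step 3: comparison with observed data.** At PV mean 2.5 and difference 0.87, with 4 rescued per arm, the size of the estimated difference is 0.82 on observed data, 0.78 under own-arm WCO and 0.74 under a pooled maximum. If only OTX-DP subjects are rescued, the figures are 0.82, 0.62 and 0.59. The own-arm rule therefore still pulls the estimate down, though by less than a common value would.

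**Step 4: no true effect.** The expected maxima are then equal, and with equal rescue counts the rule does not shift the difference. False positives favouring the drug are 1.5–2.0% (own arm) against 0.9–2.0% (pooled), all below 2.5%. With 2 OTX-DP and 6 PV subjects rescued they are 6.6–9.1% against 6.6–8.6%. That excess comes from the rescue imbalance and appears under both rules.

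**The case against.** The case against the point is substantial, and four stronger readings that a reader might infer do not survive it.

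- **That the rule is the reverse of conservative, or inflates the effect.** Step 3 shows otherwise. At PV mean 2.5 and difference 0.87, the imputed value lies about 2.0 units above the OTX-DP mean but only about 1.5 above the PV mean. With equal rescue, or rescue only in OTX-DP, WCO therefore moves the estimate against the drug. At PV mean 2.0, power is 91.4% against 95.1% on observed data. The lean exists only relative to a common value.
- **That it always favours the drug.** One OTX-DP score of 4 at that visit and time point removes any advantage. At PV mean 3.0 and difference 0.87, the maxima tie in about 78% of trials. If only PV subjects are rescued, OTX-DP gains nothing; a common 4.0 would then give a slightly larger difference (1.005 against 0.992 at PV mean 2.0, difference 0.87).
- **That WCO is the only analysis that penalises rescue.** BOCF replaces a missing score with the subject's own Visit 4a score, and entry requires itching averaging at least 3 at that visit (Protocol 5.5.2, criterion 10). That penalty does not depend on the arm's response.
- **That the trial's conclusion is exposed.** The primary and hierarchical tests use multiple imputation, and neither document makes a claim rest on WCO.

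The rule is also openly defined, so it is not a contradiction between the documents. What remains is that the penalty for rescue depends on the arm's own response. The OTX-DP maximum can even be milder than BOCF: where it is expected near 3.23, a rescued subject with a baseline of 3.5 or 4 could receive a worst case better than their own pre-treatment score.

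**Conclusion.** The point holds as a minor weakness in a supportive analysis. If OTX-DP works and some OTX-DP subjects are rescued, the own-arm maximum is expected to treat them more leniently than rescued PV subjects. Relative to a common value, the gain to OTX-DP is roughly 0.01 to 0.09 units with 4 of 40 rescued per arm, against planned effects of 0.87 to 1.13. That range rests on an assumed PV mean of 2.0 to 3.0, SD 1.0 and rescue unrelated to the score. It shrinks with fewer rescues or a higher PV mean, because the scale stops at 4. The calculations show no material effect on false positives from this rule, and the primary result does not depend on it.

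**What to change.** In SAP 8.2.1 and Protocol 10.7, replace the reference to the subject's own arm with one value used for both arms: either the maximum observed across both arms at that visit and time point, or the scale maximum of 4.0. The same edit can add the visit-and-time-point condition that the protocol text lacks. Make the change before unmasking.

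It takes a few words and needs no new data or subjects. The only downside is a slightly less favourable supportive estimate if the drug works. If the sponsor prefers to keep the own-arm rule, the common-value version could be added as a further sensitivity analysis.

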8.2.2 Imputation of Dates

Partial or missing dates will be imputed where complete dates are required to flag data as treatmentemergent or concomitant with treatment. Partial/missing start and end dates for AEs and concomitant medications will be imputed as follows:

Partial/missing start date:

- Dates with missing day only will be imputed as the 1st of the month unless the month and year are the same as the month and year of the first dose of study medication, in which case the missing day will be imputed as the first dose day of study medication.
- Dates with both day and month missing will be imputed as 1 Jan unless the year is same as the year of first dose of study medication, in which case missing day and month will be imputed as the first dose day and month of study medication.
- Completely missing dates will be imputed as the first dose date of study medication unless the end date is on or before the first dose date of study medication, in which case the missing date will be imputed as 1 Jan of the same year as the end date.

Partial/missing end date:

- Dates with missing day only will be imputed as the last day of the month unless the month and year are the same as the month and year of the last dose of study medication, in which case missing day will be imputed as the last dose day of study medication.
- Dates with both day and month missing will be imputed as 31 Dec unless the year is the same as the year of the last dose of study medication, in which case missing day and month will be imputed as the last dose day and month of study medication.
- If the ongoing flag is missing or "Yes" then the date will not be imputed unless death date is available, in which case the missing date will be imputed as the death date. If ongoing is "No" then the missing end date will be imputed as the last dose date.
- If the imputed date is after the date of death, then the end date will be set equal to the date of death.

The original dates will be displayed in data listings and the imputed dates will be used in derivations only (study day, treatment-emergence status, etc.).

8.3 Definition of Baseline

For all efficacy variables , baseline will refer to the time specific measure at Visit 4a (e.g., ocular itching at 3 minutes post-CAC at Visit 4a will be the baseline for ocular itching at 3 minutes post-CAC at Visits 6b, 6a, 5, 8b, 8a, and 7).

For all safety variables, baseline is defined as the last measurement prior to the first dose of study medication.

